#### **3.3. Additional objectives**

The additional objectives of this study are as follows:

- To investigate the demographic and social characteristics
- To investigate the family history for ALS or FTD
- To investigate the clinical classification, functional deficits, disease progression and health care measures in a subset of ALS patients with pathogenic variants in the genes of SOD1

or C9orf72 as compared to ALS patients with no ALS-associated mutations in the investigated genes

- To register available data on serum concentration of neurofilament light chain (sNfL)
- To register the history of interventions and health care measures including percutaneous endoscopic gastrostomy (PEG) and ventilation therapy
- To register the provision with assistive technology devices, symptomatic pharmacotherapy and physical, occupational and speech therapy
- To identify patient's treatment expectations towards ALS therapy using the Measure Your Medical Outcome Profile (MYMOP2)

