## **4. Overall study design**

### **4.1. Study design**

This is a longitudinal, non-interventional, non-randomized, multicenter, prospective study conducted in subjects with ALS. Duration of study participation for each subject will be up to approximately 12 months. Subjects will be enrolled to receive questionnaires, in order to assess the variables and to provide blood samples for molecular genetic testing. Approximately 1,000 subjects are planned to complete the study. It is anticipated that up to approximately 18 sites will be activated in Germany. This registry study will be reported according to STRO-BE-statement.

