### 9.3. Disease history

Data on disease history will be collected as follows. Onset of ALS will be defined at time of paresis in extremities, dysarthria or dysphagia.

Table 4: Items used to describe the disease history

Item	Description
Date of onset	MM-YYYY
Date of diagnosis	MM-YYYY
Age of onset	YY
Duration of disease	MM
Data of death (if applicable)	MM-YYYY

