## 9.7. Interventions and health care measures

Data on clinical interventions and health care measures will be collected as follows:

*Table 8: Items used to describe clinical interventions and health care measures*

Item	Description
Percutaneous endoscopic gastrostomy (PEG)	Y/N Date of provision (MM/YYYY)
Non-invasive ventilation (NIV)	Y/N Date of provision (MM/YYYY) Usage up to 8 hours per day Usage 8 to 16 hours per day Usage more than 16 hours per day
Invasive ventilation (IV)	Y/N Date of provision (MM/YYYY)
Provision of manual wheelchair (1)	Y/N Date of provision (MM/YYYY)
Provision of complex power wheelchair (1)	Y/N Date of provision (MM/YYYY)
Provision of augmented communication device (1)	Y/N Date of provision (MM/YYYY)
Provision of assistive technology (e. g. robotic arms), (1)	Y/N Date of provision (MM/YYYY)
Physical therapy (2)	Y/N Treatment units per week
Occupational therapy (2)	Y/N Treatment units per week
Speech and swallowing therapy (2)	Y/N Treatment units per week
Pharmacological therapy (3)	Riluzol, Y/N Symptomatic drugs, number of medicines

(1) Data will be obtained in a multi-center subset of up to 300 participants

(2) Data will be obtained in a single-center subset of up to 100 participants

(3) Data will be obtained in a multi-center subset of up to 200 participants

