## **11. Statistical methods and analysis plan**

Descriptive statistics will be presented for each assessment of all subjects at study visit. Subgroup analyses by genetic or clinical criteria or other baseline characteristics will be performed. Secondary endpoints in the genetically defined subsets of ALS with confirmed SOD1 or C9orf72 mutations will be compared to genetically tested patients with ALS not revealing any ALS-associated mutation in any of the tested genes. Descriptive statistics will be used for the statistical analysis (frequency in percentage, mean, median, standard deviation in  $\pm$ , interquartile ranges (Q1, Q3), and ranges (min, max). The standardized mean difference (SMD) will be applied in this study. The SMD of each measure over up to 12 months will be estimated using the change in measure between each subject's assessments and within each individual. The standardized mean difference expresses the size of intervention effect. Difference of frequencies between two groups will be assessed by Fisher's exact test or Chi-square test, or within metric data by using the Shapiro-Wilk test, Kruskal-Wallis test and Mann-Whitney U-test. The Wilcoxon test will be employed for the analysis of statistical power of ordinal-scaled data, while metric data were subjected to the t-test (ALS-FRS, MYMOP). This analysis applies to the comparison of genetically defined subsets of ALS (baseline characteristics and changes over time). The analysis of follow-up data is limited to complete

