cases, since not all patients are expected to complete end-of-study assessments due to disease progression, e.g., death. It is aimed to compare the baseline characteristics and the proportion of death between those who completed and not those not completed 6 months and 12-month assessment. Statistical significance will be ascertained by according to an error risk of up to 5% (p-value < 0.05). Associations for the clinical outcomes will be assessed by linear regression models adjusted for potential confounding factors. Results of the longitudinal observations will be also controlled for the influence of any covariate (sex, age, intervention history). Longitudinal analysis by means of group comparisons will be applied by using a multivariate analysis. 95% confidence intervals with p-values will be reported. In order to draw conclusions from the samples with censored data, missing data records will be omitted and treated as missing values. Data analysis will be performed using SPSS (Version 25.0).

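### Section 11 gives omission of records as its only rule for censored data; if the collected event dates are analysed under it, timing results depend on how long patients were observed

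*Combined protocol and SAP*

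**What the plan says.** The rule stands near the end of section 11: "In order to draw conclusions from the samples with censored data, missing data records will be omitted and treated as missing values". Shortly before it, the section restricts the analysis of follow-up to patients whose data are complete. Its explanation reads: "cases, since not all patients are expected to complete end-of-study assessments due to disease progression, e.g., death". The only planned look at non-completers is this: "It is aimed to compare the baseline characteristics and the proportion of death between those who completed" and those who did not, at 6 and 12 months. Death therefore enters as a proportion.

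The methods named in section 11 are descriptive statistics, the standardized mean difference, Fisher's exact and Chi-square tests, Shapiro-Wilk, Kruskal-Wallis, Mann-Whitney, Wilcoxon, the t-test, linear regression and an unspecified multivariate analysis. Kaplan-Meier, log-rank, Cox and competing-risk methods do not appear.

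The data items include dates. Table 8 (section 9.7) records PEG, NIV and invasive ventilation as yes/no plus "Date of provision (MM/YYYY". Table 4 (section 9.3) records month and year of onset and of diagnosis, and "Data of death (if applicable". The objective in section 3.3 is "To register the history of interventions and health care measures including percutaneous endoscopic gastrostomy (PEG) and ventilation therapy". The same section, with section 11, sets out a comparison of disease progression and health care measures between SOD1 or C9orf72 carriers and mutation-negative patients. On follow-up, section 4.1 says: "Duration of study participation for each subject will be up to approximately 12 months".

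**The concern.** A censored record is not a missing one. A patient seen at V3 without PEG has no PEG date because PEG has not happened, and the event-free time is the information that a timing analysis needs. A rule that omits the record discards it.

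If a time to PEG, NIV, invasive ventilation or death is computed with the listed methods, it is computed only in patients who already had the event. Its mean or median then reflects the observation window as much as the event rate. Genetic groups that enter at different disease durations could look different when their rates are equal, or alike when their rates differ. The SOD1 and C9orf72 comparison is where this would do harm. It is a separate matter from the loss of patients who miss visits.

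**Working it through.** **Inputs from the documents.** Follow-up is about 12 months per patient (section 4.1). PEG, NIV and tracheotomy are scheduled at V1 and V3 (Table 1). Patients consent at baseline (sections 5.2 and 8.1). No event rate, median time to an intervention, survival time or disease duration at entry is given, so there is no plan figure to reproduce. Every rate below is an assumption.

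**Check 1: time counted from V1, exponential events, T = 12 months.** Let p be the share with the event by T.

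- Rate: λ = −ln(1 − p)/T
- True median: ln 2/λ
- Median among those with the event: −ln(1 − p/2)/λ

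For p = 20%: λ = 0.2231/12 = 0.01860. The true median is 0.6931/0.01860 = 37.3 months. The event-only median is 0.1054/0.01860 = 5.7 months.

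| Assumed p | True median (months) | Event-only median (months) | Ratio |
|---|---|---|---|
| 10% | 78.9 | 5.8 | 0.07 |
| 20% | 37.3 | 5.7 | 0.15 |
| 30% | 23.3 | 5.5 | 0.23 |
| 50% | 12.0 | 5.0 | 0.42 |
| 70% | 6.9 | 4.3 | 0.62 |

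The event-only figure barely moves while the true median changes more than tenfold. Now double the rate of the 20% group (hazard ratio 2). Its event share is 1 − 0.8² = 36%. True medians are 37.3 and 18.6 months; event-only medians are 5.7 and 5.3. A real difference almost vanishes.

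**Check 2: time from onset to an intervention, by simulation.** Time to event is exponential. Time since onset at V1 is lognormal (log SD 0.6). Closure is 12 months after V1. Events before V1 count, since dates are taken from records. Competing death is not modelled.

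- True median 36, entry median 18: 54% of patients are omitted and the event-only median is about 13.5 months. Kaplan-Meier on the same data returns 36.
- True median 36 in both groups, entry medians 12 and 30: event-only medians are about 11.3 and 17.4 months, a false difference of 17.4 − 11.3 = 6.1 months.
- Over true medians 24, 36 and 60 and entry medians 12, 18 and 30: 30% to 74% are omitted, and event-only medians run from about 10 to 20 months.

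A variant with gamma-distributed disease duration at V1 (shape 2, mean 12 to 36 months) gives event-only medians at 18% to 62% of the true median.

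**Check 3: time from onset to death.** The model of check 2 is used, but only patients alive at V1 are kept, because nobody enrols after dying.

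- True median 36, entry median 18: the event-only median is about 22 months. Kaplan-Meier from onset without delayed entry gives roughly 70 months, far too long. With delayed entry at V1 it gives about 38; the small excess arises because almost nobody is under observation in the first months after onset.
- True median 24, entry median 30: the event-only median is about 29 months, longer than the truth.

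**The case against.** The strongest reply is that no timing analysis is planned. No objective or endpoint is a time to PEG, ventilation or death. Section 3.3 speaks of registering a history, group differences in yes/no items go to Fisher's exact or Chi-square test, and death is compared as a proportion. This stands. In those comparisons a patient without PEG is a complete record, counted as a no.

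Second, the sentence omits missing data records and does not say that event-free patients are missing. It follows text about patients who do not complete assessments, so censored may be a loose word for loss to follow-up. This also stands as a possible reading. A blank date is nevertheless what an event-free patient has, and the sentence offers nothing else to do with it.

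Third, the study is declared exploratory, without a formal hypothesis. That limits the consequences. It does not make omission a valid treatment of censoring.

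A reader might infer more than the documents support:

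- That the plan will report times to intervention that are far too short. It commits to no such result, and it gives no rates from which the size could be derived.
- That times to death would also always be too short. Check 3 shows that they need not be.
- That the point extends to device provision. Table 1 schedules those items at V1 only, in a subgroup, and Table 8 limits them to up to 300 participants.

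**Conclusion.** The point holds conditionally. Section 11 announces conclusions from censored samples, gives omission as its only rule and names no suitable method. If the dates of PEG, NIV, invasive ventilation or death are analysed under that rule, the results depend on length of observation. For interventions they are too short in every setting tried. With a true median of 36 months and entry at a median of 18 months since onset, the figure is about 14 months; different entry times alone produce a false difference of about 6 months. For death the direction is not fixed, and ordinary Kaplan-Meier from onset would also be wrong without delayed entry.

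These sizes rest on assumed exponential event times and assumed entry distributions, with death not modelled as a competing event for interventions. The direction for interventions does not rest on the particular rates chosen. If timing is not analysed, no planned result is biased by the rule, but the sentence then has no purpose and misleads. The change should be made; the primary objective, the frequency of genetic variants, is not touched.

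**What to change.** State whether the timing of PEG, NIV, invasive ventilation or death will be analysed.

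**If yes**, replace the sentence by: *Patients without the event at last contact are censored on that date and kept in the risk set.* Then:

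- Define the time origin and last contact. For interventions, last contact should be the last date on which status was known, since Table 1 records them at V1 and V3 but not V2.
- Analyse death by Kaplan-Meier or Cox with delayed entry at V1, or count time from V1.
- Analyse PEG, NIV and invasive ventilation by cumulative incidence or cause-specific Cox, with death as a competing event. For events after V1, let patients enter the risk set at V1.
- Do not report means or medians of time among patients with the event only.

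**If no**, delete the sentence and state that only proportions are reported.

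The cost is a wording change and standard survival procedures on event dates already collected. One small downside is that some medians will not be reached within about 12 months of follow-up; the 12-month cumulative incidence can be given instead.

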## **12. Ethical and legal principles**

### **12.1. Ethical and regulatory requirements**

APST must comply with all instructions, regulations, and agreements in this protocol and applicable ICH and GCP guidelines and conduct the observational study according to local regulations. The Investigator may delegate responsibilities for study-related tasks where appropriate to individuals sufficiently qualified by education, training, and experience, in accordance with applicable ICH and GCP guidelines. The Investigator should maintain a list of the appropriately qualified persons to whom significant study-related duties have been delegated.

### **12.2. Responsibilities of the investigator**

The observational study is realized in collaboration of APST and Charité – Universitätsmedizin Berlin. The study protocol will be approved by the Independent Medical Ethics Committee (IEC) of the Charité – Universitätsmedizin Berlin, Germany. The protocol, and other required study documents must be approved prior to starting the study. It is the responsibility of the investigator to ensure that all aspects of institutional review are conducted in accordance with current governmental regulations. APST must receive a letter documenting ethics committee approval, which specifically identifies the amendments prior to the initiation of the study.

### **12.3. Informed consent procedures**

#### **12.3.1. Informed consent procedures of study participants**

Prior to any data collection informed consent will be obtained from all eligible and participating patients. Information about the study and that study participation is voluntary will be explained to the subject. The informed procedure will be organized in a multi-step process of 1) patient information, 2) genetic counselling prior to study participation, 3) written informed consent and selection of modalities for the notification of genetic study results. The patient information encompasses the option, that study participants are, however, entitled to refuse genetic counselling in writing, if they have already been informed about its content. The study information and the offered genetic counselling will address the potential medical, psychological and social burden that may be associated with pathogenic gene mutations as well as the individual or societal benefits aimed with the study. Participating patients will decide to provide blood samples for the following research purposes:

- Use for exclusive analysis of the genes SOD1, C9orf72, FUS and TARDBP as defined in this protocol
- Optional and future use for analysis of other known ALS-related genes
- Optional and future use for the search of still unknown ALS-related genes

The subject must be given sufficient time to consider, whether to participate in the study. A copy of the informed consent, signed and dated by the subject, will be given to the subject. Confirmation of a subject's informed consent will also be documented in the subject's medical record prior to any data collection under this protocol. The signed informed consent will be retained with the study records. The informed consent procedure will be performed in alignment with the "Genetic Diagnosis Act" (Gendiagnostikgesetz, GenDG).

Given the potential, diagnostic and therapeutic relevance of individual study results on genetic variants of SOD1, C9orf72, FUS and TARDBP genes, all study participants are offered the principal option to be informed about the result of genetic investigation. Conversely, the knowledge and awareness about own study results – encompassing the potential implications for genetically related family members – might be perceived as psychologically burdensome. Therefore, study participants will be informed about the requirement to select between notification options of their individual study results. Study participants who decided to be notified about the genetic study results are offered to seek genetic consultation prior to the notification of study results. The offered genetic consultation will include the information on the mutation type, the interpretation of results (benign, likely benign, likely pathogenic, pathogenic or variant of uncertain significance) as well as the potential medical, psychological and social implications of the findings. The procedure of genetic counseling is described in more detail in section 12.3.3. Study participants will be informed that genetic study results of uncertain significance may be discussed within the genetic review board which is described in section 10.3. The patient's directive concerning the notification about the individual study results is subject to the study information and mandatory part of the informed consent. Study participants are requested to select one of the following options of notification about individual study results:

- No notification about genetic study results
- Notification about all genetic study results
- Notification about selected genetic study results with therapeutic relevance

Patients who refuse to be notified about study results will not be informed about the outcome of genetic analysis. This patient's directive explicitly includes pathogenic mutations that might be of diagnostic or therapeutic relevance. The patient's directive of notification of all genetic study results will include normal findings (no or benign variants) genetic, genetic variants of unknown significance and pathogenetic mutations (likely pathogenic or pathogenic genetic variants in the investigated genes of SOD1, C9orf72, FUS and TARDBP. Results of diagnostic relevance are defined as genetic variants being known to cause ALS or can increase the risk of ALS or can modify the phenotype of the disease including the progression rate. The finding of pathogenic variants can lead to the diagnosis of fALS although the disorder – given the negative family history of ALS – has prior been classified as sALS. The diagnostic relevance can extend to other family members as likely pathogenic or pathogenic mutations in the study at ALS genes might substantiate a genetic risk for ALS to first- and second-degree relatives of study participants. Therapeutic relevance is defined by the planning or performance of a phase 3 clinical trial, a planned or ongoing early access program or an expected approval of genetic medicine targeting one of the studied genes within the next 12 months. Currently, therapeutic relevance can be stated for mutations found in the SOD1 gene. Therapeutic relevance of C9orf72 and FUS can be expected within the next few years post-approval of this study protocol. The definition of diagnostic and therapeutic relevance and the scheme of notification of individual study results is provided in table 11.

### 12.3.2. Genetic consultation on genetic study results

All study participants are offered the principal option to seek genetic consulting. Genetic counseling on study participation (prior to genetic testing) and prior to the notification of study results (after genetic testing) will be differentiated (Table 11). The counseling prior entering the study will be performed by the study neurologist. However, under certain circumstances, such as the family history of fALS, the additional counseling by a neurologist being certified for genetic counseling or by a certified geneticist can be required. The consultation prior participating in the study will include the potential medical, psychological and social implications that can be associated with pathogenic gene mutations as well as the potential individual treatment options indicating gene-specific treatment options, which are available or in clinical development.

Study participants will be offered a genetic consultation on the genetic study results. In principle, study results showing no genetic variants or benign variants will lead to the study neurologist consulting about the specific results. In contrast, study results of *likely pathogenic* or *pathogenic mutations* will be primarily consulted by the study neurologist, in order to refer the patient to a specialized neurologist being certified for genetic counseling or to a certified geneticist. Recruiting study sites are prepared to refer patients (or their advice seeking relatives) to certified geneticists who are experienced in the consultation on genetic variants in ALS. In preparation of external genetic consultation, patients are provided with a sealed envelope containing the pseudonymized study results. Subsequently, the patient will forward the envelope to the genetic consultant. The genetic consultant can contact the study center for additional clinical information and might decide for an independent genetic investigation, in order to confirm the study results. The confirmation can be done by retesting or, preferably, by means of de-pseudonymization of study results. As authorized by the study participant – upon request of consulting geneticist – the genetic study results might be de-pseudonymized by the study center. Based on the de-pseudonymization order, the unblinded genetic report on SOD1, C9orf72, FUS and TARDBP will be provided by genetic laboratory and used for genetic consultation. The unblinded genetic results are suitable for genetic consulting, such as the laboratory ARCHIMED Life Science GmbH (ARCHIMEDlife, Vienna, Austria). ARCHIMEDlife complies to all required certifications for genetic analysis (including ISO15189). Thus, the genetic results – primarily generated for research purposes – allow the unrestricted use for genetic counseling.

Table 11: Differentiated notification of study results in relation to patients' directives

Informed consent	Genetic consulting prior study participation	Patient's directive on notification about genetic results	Genetic result	Genetic consulting on genetic results
informed consent of all patients as obtained by study neurologist	refusal of genetic consultation	no notification about genetic results	not applicable	not applicable
	genetic counseling on the po-	notification about all genetic results	
 
• no variant
 
• benign variant
 
	counseling by study neurologist

	
tential burden of pathogenic gene mutations and the potential diagnostic and therapeutic measures as offered by study neurologist (sALS) or certified geneticist (fALS)
		
 
• uncertain significance
 
• likely benign
 
• likely pathogenic
 
• pathogenic
 
	counseling by study neurologist followed by geneticist
		notification about genetic results with therapeutic relevance	
 
• likely pathogenic
 
• pathogenic variant with treatment option
 
	counseling by study neurologist followed by geneticist

